The new questionnaire consists of 38 questions on an individual's dietary intake across 17 product groups. The questionnaire and cutoff values are based on the Guidelines for Healthy Diet (Kromhout et al., 2016), where applicable further refined using the recommendations of the Netherlands Nutrition Centre. After completing the questionnaire, a profile wheel (see Figure 1) is displayed, providing insight into compliance with the guidelines for 17 product groups. In this profile wheel, a “traffic light” color is used for each product group to indicate whether an individual roughly meets the guidelines (green), consumes more than 50% of the recommended amount (orange), or consumes less than 50% of the recommended amount (red). For (sub)product groups for which no guideline exists, a grey color is shown (for example, for potatoes).

[figure not shown]

Figure 1. Example of a “Profile wheel” for an individual after filling out the Nutri-plus module.

The product groups defined by the Health Council were further refined to provide participants with more detailed insight into areas of their dietary pattern that could be improved. In addition, unhealthy choices are included in the Nutri+ module, even though they are not part of the Guidelines for Healthy Diet (Gezondheidsraad, 2015). By assessing and displaying these in the profile wheel, individuals can also gain insight into the extent of their unhealthy choices.

With the Nutri+ module, we aim to offer a dietary intake assessment as an integral part of the 360-degree tool, enabling individuals to gain insight into their own dietary patterns and areas for improvement. These outcomes can be used to provide personalized dietary advice or interventions tailored to the individual.

Before the Nutri+ module can be used for personalized dietary assessment and advice, it must be evaluated to determine whether it provides an accurate picture of an individual's dietary intake. To this end, the outcomes of the Nutri+ module, consisting of a red–orange–green categorization, can be compared with those of an already validated method for dietary intake assessment. In the literature, (weighed) dietary recall methods are commonly used to validate dietary questionnaires (Cade, 2002), as these methods are less sensitive to underreporting than food frequency questionnaires (Prentice, 2011).

In a 24-hour recall method, individuals are asked to provide detailed information about all foods and beverages consumed in the previous 24 hours (Meijboom, 2017). To obtain a reliable estimate of habitual dietary intake, the 24-hour recall must be repeated on multiple days in order to correct for day-to-day variation. Wageningen University & Research has developed and validated a Dutch online 24-hour dietary recall method that can be completed entirely online by participants, known as “Compl-Eat” (Meijboom, 2017). This significantly reduces the costs and burden for both researchers and participants.

This study will consist of two phases. The first phase will involve a pre-test to assess the usability, comprehensibility, and completeness of the developed Nutri+ module among end users and experts. The insights generated will be used to further improve the Nutri+ module and the profile wheel visualization. After completion of the first phase, the second phase will commence, in which the Nutri+ module will be compared with a reference method in an evaluation study. The selected reference method for this evaluation study is a 24-hour recall using Compl-Eat.

2 Goal

Goal of the Nutri+ module: To assess, at the individual level, the extent to which a person complies with the dietary guidelines and where there is room for improvement. These insights are used to provide personalized dietary advice and to monitor an individual's dietary intake.

Phase 1: Pre-test

Objectives

- To gain insight into the user experiences of the target group with completing the questionnaire and with regard to the visualization of the profile wheel.
- To collect feedback from experts on the Nutri+ module (including completeness, question formulation, example products, etc.).
- To use the collected user insights and expert feedback to further improve the Nutri+ module and the profile wheel visualization before starting the second phase of the study (the evaluation study).

Phase 2: Evaluation study

Main objective: To evaluate whether the absolute intake in grams, as measured by the Nutri+ module, is comparable to Compl-Eat for the 21 product groups. This will be explored both quantitatively (e.g., what percentage of intake is covered by the Nutri+ module compared with Compl-Eat) and qualitatively (e.g., where the differences between Compl-Eat and the Nutri+ module lie). These insights can be used to further improve the tool.

Sub-objectives:

- To investigate whether the results of the Nutri+ module are reproducible over time or whether time effects are present, with a correlation coefficient of ≥ 0.75 between two measurement points considered successful.
- To evaluate the Nutri+ module (dietary questionnaire) against the Compl-Eat 24-hour recall method. Specifically, we aim to examine whether the Nutri+ module can accurately classify at least 75% of individuals into three categories for the 21 product groups.
- To evaluate the visualization of the profile wheel by users of the Nutri+ module.

3 Study design

This is a longitudinal randomized study to evaluate the Nutri+ dietary intake module. The Nutri+ module can be completed by participants at home via an online portal; it is filled out only once and takes approximately 30 minutes to complete. As a reference method, Compl-Eat is used. This is an online 24-hour recall method developed by Wageningen University & Research (Meijboom et al., 2017). Participants in the study can complete this 24-hour recall themselves at home via a portal, recording everything they ate and drank in the previous 24 hours. Based on the submitted data, the Compl-Eat platform can determine for an individual how much and what was consumed at both the product group and individual product levels. Compl-Eat is completed by participants on four non-consecutive days—three weekdays and one weekend day (Saturday or Sunday)—to obtain an accurate representation of an individual's average intake. The 24-hour recalls are manually checked for completeness by a researcher afterwards.

A randomized cross-over design is used, in which one group of participants completes the Nutri+ module first, while the other group completes Compl-Eat first. The days on which participants complete

the Nutri+ questionnaire and the days on which Compl-Eat is completed are randomly selected. There is a minimum interval of 7 days between the Nutri+ module and the first or last day of Compl-Eat.

In addition, possible time effects in dietary recording and the reproducibility of the Nutri+ module results are examined. To this end, participants are invited again after three to six months to repeat the entire procedure of completing the Nutri+ module once and Compl-Eat four times. The first series of questionnaires is sent out in April; the second series begins in September.

See Figure 2 for a schematic overview of the study design.

[figure not shown]

Figure 2. Schematic overview of the study design of the evaluation study.

4 Study population

A total of 200 participants will be recruited for this study. The target population consists of healthy men and women aged 35 to 80 years with normal weight, overweight, or obesity.

Inclusion criteria for this study are:

- BMI ≥ 20 and < 40 kg/m².
- Age 35–80 years.
- Good command of the Dutch language.
- Reasonable digital literacy and access to a PC or laptop.
- A fairly typical Dutch dietary pattern.

Exclusion criteria for this study are:

- Pregnant women or women who are breastfeeding.
- Recent unintentional weight loss of more than 5 kg.
- Under treatment for a serious (chronic) illness.
- History of myocardial infarction or stroke in the past 5 years.
- Previous or planned bariatric surgery.

In this study, we aim to perform subgroup analyses to examine whether there are differences in the usability of the Nutri+ module between men and women, across different age groups, between low and high socioeconomic status, and between individuals with normal weight and those with overweight or obesity. The rationale for this is the known differences in dietary intake among these subgroups and the potentially higher risk of over- or underreporting. Therefore, during recruitment, we will strive for a proportional distribution of sex (male/female), age (35–55 / 55–80), educational level (primary/secondary vocational or higher education/university), and BMI (20–25 / 25–30 / 30–40) in the study population. For sex, this will already be considered during screening: once 100 participants of a particular sex are recruited, only participants of the other sex will be admitted.

Recruitment will mainly take place via social media platforms (Facebook, LinkedIn, Instagram). If necessary, recruitment will be expanded through other channels, such as local newsletters and websites (e.g., “In de Buurt”). The number of participants represents our minimum target for data collection to ensure valid and reliable outcomes and to allow for subgroup analyses. Recruitment will therefore continue until the minimum number of participants is reached; additional participants are welcome (up to a maximum of 300). There will be no reserve participants.

5 Description of the study

First Phase

The first phase consists of preparatory activities, including the development of the Nutri+ module. During this phase, a pre-test is conducted with both participants and experts, which can take place either online or in person at a TNO location, depending on whether a visit to TNO is feasible. The aim of this pre-test is to assess the usability and comprehensibility of the Nutri+ module through a think-aloud protocol supervised by a researcher. This method involves asking participants and experts to verbalize all their thoughts, feelings, and opinions while performing a task. This provides the researcher with deeper insights into the user experience, the interpretation of the questions, the respondent's thought process, as well as the completeness of the questionnaire, the alignment of response options with the questions, and the overall clarity and understandability of the questionnaire.

The think-aloud protocol is preferably conducted in a (digital) environment where the end user/respondent would normally complete the questionnaire; if this is not possible, it can also be carried out in a secluded, neutral room at TNO. Before starting, the researcher provides the participant or expert with an introduction to the study and requests consent for audio recording. The researcher remains passive while the participant or expert completes the questionnaire, but may remind them to continue verbalizing their thoughts if they fall silent. After completing the think-aloud protocol, several additional questions are asked regarding the experience of completing the questionnaire and the visualization of the profile wheel.

Both the target population of the Nutri+ module and a number of experts are involved in the pre-test. In total, approximately 10 participants are aimed for. Among the target population, the goal is to include a group with diverse characteristics in terms of age, sex, and educational level. Based on the results of this pre-test, the Nutri+ module will be further refined to prepare it for use in Phase 2.

Table 1: Overview timeline and investment for participants pre-test

	How often and when	Total time investment
Go through the think-aloud protocol	1 time filling out Nutri+ module (spring 2022)	1 time 30 minutes
Answering additional questions	1 time directly after filling out Nutri+ module (spring 2022)	1 time 15 minutes

Second Phase

The second phase involves recruiting participants through social media campaigns and the completion of the Nutri+ module and Compl-Eat. Participants are recruited via social media advertisements, which link them to an online information sheet. After reading the information sheet, participants can provide online informed consent for participation in the study. They are then automatically directed to an online screening questionnaire (see inclusion and exclusion criteria). This screening questionnaire automatically assesses whether the individual meets the study's selection criteria. Candidates who do not meet the criteria are informed immediately. Candidates who do meet the criteria are directed to a baseline questionnaire to collect various baseline data (medication use, physical activity, adherence to any dietary or nutritional rules, and allergies or intolerances). Participants are then informed about the further study schedule and procedures.

The study uses a cross-over design, in which participants are randomly assigned to one of two sequences: starting with the Nutri+ module or starting with Compl-Eat. Participants who start with the Nutri+ module during the first series (autumn 2022) will start with Compl-Eat during the second series (spring 2023), and vice versa.

For all participants, the days on which the Nutri+ module and Compl-Eat must be completed are randomly selected. Both the Nutri+ module and Compl-Eat are completed at home using login credentials for the respective online platforms. Participants are not informed of the full schedule in advance to minimize potential influence on their dietary behavior. One day before a participant's first "assessment day," they are contacted by email by a researcher, requesting that they complete either the Nutri+ module or Compl-Eat the following day. Participants can respond to this email if the scheduled day does not fit their personal planning. In that case, the researcher reschedules the assessment day, and the participant is contacted again at a later time.

During the first series (autumn 2022), all participants complete Compl-Eat on four days within a two-week period and complete the Nutri+ module once. A minimum interval of seven days is maintained between completing Compl-Eat and the Nutri+ module to prevent interference between the methods.

After completing the first series (autumn 2022), participants are reminded that they will be contacted again in spring 2023 to complete the Nutri+ module and Compl-Eat. The same procedures are followed in spring 2023 as in autumn 2022.

Participants are also asked to complete an evaluation questionnaire regarding their experiences with completing the questionnaire and the visualization of the dietary profile wheel.

After data collection for the evaluation study is completed, the data are analyzed. Based on this analysis, recommendations will be made for adjusting the Nutri+ module (questionnaire, algorithms, and cut-off values) and for improving the visualization of the profile wheel.

Tabel 2: Overview timeline and investment for participants evaluation study

	How often and when	Total time investment
--	--------------------	-----------------------

Nutri+ module	1 time filling out autumn 2022 1 time filling out spring 2023	2 times, 20 minutes. 40 minutes in total.
Compl-eat	1 time 4 days filling out autumn 2022 1 time 4 days filling out spring 2023	80 minutes per time. 160 minutes in total.
Evaluation questionnaire	1 time filling out	15 minutes

6 Outcome variables

To evaluate the Nutri+ module in comparison with Compl-Eat, it is first necessary to assess the extent to which the food groups used in the Nutri+ module are also available in Compl-Eat. The outcomes listed below depend on the results of this mapping. In addition, Compl-Eat will need to apply the same food group classification based on the same cut-off values per product group as used in the Nutri+ module.

Primary outcomes

- Intake in grams for the 17 product groups that are quantitatively assessed (Fruit, Vegetables, Legumes, Nuts and Seeds, Fish, Dairy, Meat, Eggs, Soft Drinks, Alcohol, Coffee, Tea, Snacks, Sweet Spreads, Chips/Nuts/Party Snacks, Fast Food, Desserts/Ice Cream/Cakes) for both Compl-Eat and the Nutri+ module.

Secondary outcomes

- Evaluation overall and by subgroup (sex, BMI, etc.) for all product groups available in both Compl-Eat and the Nutri+ module, for which guidelines exist to assess reproducibility and classification. For Nutri+, these include: Fruit, Vegetables, Butter and Cooking/Frying Products, Dressings and Oils, Legumes, Nuts and Seeds, Fish, Dairy, Meat, Eggs, Cereal Products, Potatoes, Soft Drinks, Alcohol, Coffee, Tea, Snacks, Sweet Spreads, Chips/Nuts/Party Snacks, Fast Food, Desserts/Ice Cream/Cakes.
- Energy intake based on Compl-Eat
- Expected energy intake based on sex, age, weight, and physical activity
- Evaluation of the profile wheel

7 Description of incidents, safety, adverse events, side effects

The study for participants consists of completing dietary questionnaires and 24-hour dietary recalls. Due to the nature of the study, no incidents or adverse events are expected. Any complaints regarding the conduct of the study, the websites used, or other questions or remarks can be submitted via email or telephone, as indicated in the participant information.

8 Data-analysis and statistics

For Compl-Eat, all analyses will be based on the average intake per product group across the four assessment days within a single measurement series (spring or autumn).

Based on the Compl-Eat data, it will be assessed whether there is excessive under- or over-reporting in the study population. To this end, the number of calories consumed, as calculated by Compl-Eat, will be compared with the expected caloric intake based on participants' age, sex, height, and weight.

The agreement between classifications in Compl-Eat and the Nutri+ module will be evaluated by assessing the percentage overlap in categorization and subsequently examining correlations between the scores. The goal is for 75% agreement per product group between the Nutri+ module and Compl-Eat. If lower agreement is observed, the data will be qualitatively examined to identify areas for improvement in the Nutri+ module.

In addition, the intake in grams per product group as measured by the Nutri+ module and Compl-Eat will be examined. Correlation coefficients will be calculated to assess agreement between the Nutri+ module and Compl-Eat. These outcomes are primarily exploratory and aim to provide insight into where the largest differences between Compl-Eat and Nutri+ occur. These insights can be used to further improve the Nutri+ module.

To assess the reproducibility of the Nutri+ module, correlations between the spring and autumn measurements will be used.

Participants' opinions on the visualization of the profile wheel will be evaluated using descriptive information.

9 Risk analysis relating to the conduct of the study

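### The plan does not say whether the traffic-light wheel is withheld during phase 2; if shown on completion, it precedes the Compl-Eat recalls in half of the within-series comparisons and precedes every Nutri+ retest, and Section 8 does not use the randomised order

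*Combined protocol and SAP*

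**What the plan says.** The introductory text before Section 2 describes what happens when someone finishes the module: "After completing the questionnaire, a profile wheel (see Figure 1) is displayed, providing insight into compliance with the guidelines for 17 product groups". Each product group is coloured green, orange or red. The text gives the purpose as "enabling individuals to gain insight into their own dietary patterns and areas for improvement".

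Section 3 sets out the comparison: "A randomized cross-over design is used, in which one group of participants completes the Nutri+ module first, while the other group completes Compl-Eat first". Section 5 (Second Phase) adds that those who begin with Nutri+ in the first series "will start with Compl-Eat during the second series (spring 2023), and vice versa". On separation of the methods, Section 5 says: "A minimum interval of seven days is maintained between completing Compl-Eat and the Nutri+ module to prevent interference between the methods". The full schedule is also kept from participants so as not to influence what they eat.

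Phase 2 participants do see the wheel at some point, since Section 5 states: "Participants are also asked to complete an evaluation questionnaire regarding their experiences with completing the questionnaire and the visualization of the dietary profile wheel". Table 2 lists that questionnaire once and does not tie it to a series.

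Section 2 sets two numerical goals: a correlation of at least 0.75 between two Nutri+ measurements, and correct classification of at least 75% of individuals. Section 8 plans percentage agreement, correlations between methods, a spring-autumn correlation for Nutri+, a check of reported energy and a descriptive evaluation of the wheel. None of these is split by, or adjusted for, sequence or order.

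**The concern.** The wheel is personal feedback against the guidelines, designed to show people where they could eat better. If it is displayed as described, a participant in a Nutri+-first series receives it before the Compl-Eat recalls. The reference method may then measure a diet, or a way of reporting it, that the index method has altered. The seven-day interval may limit memory of earlier answers, but it also leaves time for diet to change.

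The retest has the same difficulty: the second Nutri+ always follows a first. Section 2 asks whether results are reproducible or whether time effects are present, and a response to feedback could not be told apart from either.

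At stake are the main gram comparison, both numerical goals, and the changes to questionnaire, algorithms and cut-off values that Section 5 says will be based on the analysis. A feedback effect could be mistaken for a fault in the module, or could hide one.

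**Working it through.** The plan has no figure of its own to reproduce here: it states no power, alpha or effect size. The check is a count of exposures followed by illustrations.

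**Inputs.** From the documents: 200 participants (Section 4, a minimum), two sequences, two series, order swapped in the second series (Section 5). Assumed: 1:1 allocation (the ratio is not stated) and display of the wheel on completion in phase 2. Sections 3 and 5 give different seasons for the two series, so they are called series 1 and 2 here; the counts are unaffected.

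**Exposure by cell, 100 per sequence.**

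| Sequence | Series | Order | Wheel between methods | Compl-Eat after any wheel |
|---|---|---|---|---|
| A | 1 | Nutri+, then Compl-Eat | yes | yes |
| A | 2 | Compl-Eat, then Nutri+ | no | yes (from series 1) |
| B | 1 | Compl-Eat, then Nutri+ | no | no |
| B | 2 | Nutri+, then Compl-Eat | yes | yes |

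- Wheel between methods: (100 + 100)/400 = 50%. Among completers this holds for any allocation ratio, since each has one series in each order. With 20% of each sequence lost before series 2 it is (100 + 80)/360 = 50%.
- Series 1 alone: 100/200 = 50% at 1:1; 40% to 60% for allocations of 80:120 to 120:80.
- Compl-Eat after any earlier wheel: 300/400 = 75% (70% to 80% over the same allocations). Only Compl-Eat-first in series 1 has no earlier wheel.
- Nutri+ retests after an earlier wheel: 200/200 = 100%.

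**Agreement (illustration, effects assumed).** If feedback changes agreement by a net d points in exposed comparisons and the two series are pooled, the pooled figure changes by 0.5 × d.

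- 80% unexposed and 70% exposed: 80 − 0.5 × 10 = 75.0%.
- 80% and 65%: 80 − 0.5 × 15 = 72.5%, below the goal.
- The sign may be the other way. With 72% unexposed and 82% exposed, 72 + 0.5 × 10 = 77%, above the goal.

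**Retest (illustration, effects assumed).** Let r0 be the correlation without feedback, b the extra regression of the second score on the first, and s the SD of random diet change in units of the score SD. Then r = (r0 − b)/√[(r0 − b)² + 1 − r0² + s²]. With r0 = 0.80:

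- b = 0, s = 0 (the same shift for everyone): r = 0.80, unchanged.
- b = 0, s = 0.3: 0.80/√1.09 = 0.77.
- b = 0.1, s = 0.3: 0.70/√0.94 = 0.72.
- b = 0.2, s = 0.3: 0.60/√0.81 = 0.67.

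Only change that differs between people moves the correlation; the last two cases fall below 0.75.

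**What an analysis by order could show** (two-sided 0.05, 80% power, 100 v 100, no dropout, all assumed). Detectable order effect on the Nutri+ minus Compl-Eat difference within one series: 2.80 × √(2/100) = 0.40 SD. For agreement near 75%, the 95% interval for the order difference has half-width 1.96 × √(2 × 0.75 × 0.25/100) = 12 points. Power is 0.12 for 75% v 70%, 0.34 for 75% v 65% and 0.62 for 75% v 60%. A non-significant test would therefore not be reassuring; the estimate and its interval are what to report.

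**The case against.** The strongest reply is that the timing of the wheel in phase 2 is inferred. The only statement of it is in the introductory text, which describes the module in general. No phase 2 section says when study participants see it. One evaluation questionnaire, described after the spring 2023 procedures, is compatible with a single showing at the end. Figure 2 could not be checked. A reader might infer that half the comparisons and every retest are in fact contaminated; the documents do not support that. They support a conditional statement: this follows if the module behaves in the study as described, and nothing says that it does not. The sponsor took care to limit influence on diet in other ways, so silence about the wheel needs filling.

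A reader might also infer that the order was randomised to deal with interference and then left unused. The protocol attaches that purpose to the seven-day interval and gives no reason for randomising the order.

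The swap is a genuine strength: each completer contributes one comparison in each order. Pooling then averages a feedback effect without removing it, and the swap does nothing for the retest. Section 8 does not say whether the series will be pooled, but a single series alone would still be about half exposed at 1:1.

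The consequences are also milder than a failed trial. Agreement below 75% leads to qualitative examination, and Section 8 calls the gram outcomes primarily exploratory. Repeating Compl-Eat in both series gives some view of real dietary change. These points lower the severity; they do not remove the gap.

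**Conclusion.** The concern holds in conditional form. As written, the module shows its wheel on completion and no phase 2 text withholds it. If it is shown then, 50% of within-series comparisons have the wheel between the methods and 100% of retests follow an earlier wheel, while Section 8 has no analysis that would reveal an effect. The 50% assumes participants complete both series or drop out equally from the two sequences.

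The documents do not show that agreement or reproducibility is biased, by how much, or in which direction. The shifts in agreement and correlation above rest on assumed effects and show only that moderate changes could carry a result across either threshold. Should-fix: the bias is plausible and cheap to prevent, but no go/no-go decision depends on the results. If the study portal already hides the wheel, a sentence saying so settles the exposure question; the analysis by order would still be missing.

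**What to change.** 1. **Section 5.** State that the wheel is hidden until the participant's last series 2 assessment, Compl-Eat or Nutri+ as the order dictates, and is then shown together with the single evaluation questionnaire in Table 2.

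2. **Section 8.** Report percentage agreement and the Nutri+ minus Compl-Eat difference per product group by randomised order within each series, with the order difference and its confidence interval. Say that this difference mixes feedback with other order effects, such as practice from four recalls before Nutri+. In series 2 without delayed display, both orders would also have an earlier wheel behind them.

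3. **If the wheel cannot be delayed.** Report the series 1 Compl-Eat-first group as a sensitivity analysis with no earlier wheel. Report the between-series change in Compl-Eat beside the Nutri+ retest correlation, and state that the retest then has no feedback-free comparison.

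**Cost.** Step 1 needs a change to the display; the documents do not say whether the portal allows it. Participants wait for their feedback, and those who are Nutri+-first in series 2 judge the wheel at least a week after answering. Opinions on the wheel would come mainly from completers unless leavers are shown it on exit. Step 2 is extra tabulation of data already planned. Step 3 rests on about 100 of 200 participants at 1:1, which leaves little for subgroups, and it does not repair the retest.

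### The reproducibility criterion is a correlation of at least 0.75 with the correlated quantity unstated, and the plan has no measure of how many people get the same colour twice

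*Combined protocol and SAP*

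**What the plan says.** The first Phase 2 sub-objective (Section 2) asks whether Nutri+ results are reproducible over time, "with a correlation coefficient of ≥ 0.75 between two measurement points considered successful". Section 8 gives the whole analysis in one sentence: "To assess the reproducibility of the Nutri+ module, correlations between the spring and autumn measurements will be used". The type of coefficient is not named, nor is the quantity it is computed on.

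The introduction describes "the outcomes of the Nutri+ module, consisting of a red–orange–green categorization", with fixed cut-offs at roughly half and all of the recommended amount. Section 2 sets the purpose at the level of the individual and adds: "These insights are used to provide personalized dietary advice and to monitor" a person's intake.

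Agreement in colour does appear in the plan, but only between methods. Section 8 states: "The goal is for 75% agreement per product group between the Nutri+ module and Compl-Eat". Section 6 mentions reproducibility and classification together when it lists the product groups to be evaluated, but it gives no retest agreement statistic or threshold.

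**The concern.** A correlation describes how well participants keep their relative position. A user of the module receives a colour set by fixed cut-offs. How often that colour is the same on retest depends on the correlation and also on how users are spread over the three colours, so one correlation threshold corresponds to quite different rates of colour change in different product groups.

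The claim that the module is reproducible is at stake. If a user's colour changes between two uses, whoever interprets it needs to know how often that happens on retest. Both series will supply the data, but the plan does not produce the figure. The results are also meant to guide changes to the questionnaire, algorithms and cut-off values (Section 5), and a correlation does not show which cut-offs people cross.

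**Working it through.** The plan has no calculation behind 0.75, so there is no figure of its own to reproduce. The question is what a correlation of 0.75 implies for colours.

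**Inputs from the document.** Threshold 0.75 (Section 2); three colours with fixed cut-offs (introduction); 200 participants (Section 4); retest after three to six months (Section 3).

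**Assumptions.** The document gives no colour distribution, so a range of splits is used. Gram intakes X and Y in the two series are taken as bivariate normal with correlation r, the same mean and the same cut-offs.

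**Formula.** With cut-offs c1 and c2 set by the split, c0 = −∞ and c3 = +∞:

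P(same colour) = Σ over k = 1 to 3 of P(c(k−1) < X ≤ c(k) and c(k−1) < Y ≤ c(k)).

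For equal thirds and r = 0.75 the three diagonal cells are 0.229 + 0.156 + 0.229 = 0.614, so 1 − 0.614 = 38.6% change colour.

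The last column covers the other reading, in which 0.75 is the correlation of colour codes scored in steps of one. There the underlying r is first solved so that the codes correlate at 0.75.

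| Colour split (%) | Same colour, gram r = 0.75 | Change colour | Gram r needed for 75% same colour | Same colour, code correlation 0.75 |
|---|---|---|---|---|
| 33/33/33 | 61% | 39% | 0.91 | 70% |
| 50/30/20 | 64% | 36% | 0.89 | 72% |
| 25/50/25 | 64% | 36% | 0.88 | 75% |
| 60/25/15 | 68% | 32% | 0.86 | 75% |
| 20/60/20 | 68% | 32% | 0.84 | 80% |
| 70/20/10 | 73% | 27% | 0.79 | 80% |
| 80/15/5 | 80% | 20% | below 0.75 | 86% |
| 90/8/2 | 89% | 11% | none (met at r = 0) | 93% |

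**Sensitivity to the model.** With lognormal intake cut at 50% and 100% of a guideline (coefficient of variation 0.4 to 1.0, mean 0.5 to 1.25 times the guideline), 22% to 35% change colour. A mean shift of 0.5 SD between series raises the equal-thirds figure from 39% to 44%.

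**Is a pass with modest colour retention only a borderline event?** By Fisher's z with n = 200 and a true gram correlation of 0.80:

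P(observed r ≥ 0.75) = Φ[(atanh 0.80 − atanh 0.75) × √197] = Φ[(1.0986 − 0.9730) × 14.04] = Φ(1.76) = 0.96.

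At r = 0.80 the same-colour share is 65% (33/33/33), 67% (50/30/20), 71% (60/25/15) and 75% (70/20/10). So a group with a near-certain pass can still have about a third of users changing colour if users are spread over the colours. This takes all 200 as completing both series.

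**Would raw agreement alone be a better rule?** For a 90/8/2 split with zero correlation, chance agreement is 0.90² + 0.08² + 0.02² = 0.810 + 0.0064 + 0.0004 = 81.7%. That group would pass a 75% rule with no reproducibility at all.

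**The case against.** The case on the other side has several parts that stand.

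- **Colour scores may be what is correlated.** A reader might infer that the rule takes no account of colours. The text does not support that: Section 8 mentions correlations between scores when it compares classifications, and for reproducibility it leaves the quantity open. On colour codes, retention for the splits from 33/33/33 to 70/20/10 is about 70% to 80%. Even so, a correlation of codes is not an agreement rate.
- **The colour splits are assumed.** For strongly skewed groups the share changing colour falls to 20% or 11%. Most changes are also to the neighbouring colour: at gram r = 0.75, red-green swaps are about 3% or less in the splits tabulated.
- **The 75% goal is not a retest standard.** It is tempting to say that a group could fail the study's own standard against itself. Sections 2 and 8 set that goal only for Nutri+ against Compl-Eat, and the document sets none for retest.
- **Colour change is not all noise.** Over three to six months some diets will truly change. The data cannot separate this from measurement error, and it lowers the correlation as well.
- **Grams are a legitimate basis.** The main objective and primary outcome are in grams, and the cut-offs may yet be revised.

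These points limit the size and wording of the concern, and they rule out replacing the correlation with a raw agreement rule. They do not supply the missing figure on how often a user's colour is the same on retest.

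**Conclusion.** The point holds as a gap in specification and reporting. The reproducibility criterion does not say what is correlated, and no planned statistic shows how many people keep their colour, although that is the module's output for the individual. Over splits from 33/33/33 to 70/20/10, a correlation of 0.75 goes with 27% to 39% changing colour if grams are correlated, and about 20% to 30% if colour codes are. Taken together, that is roughly 2 to 4 in 10 users, and fewer in strongly skewed groups.

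The figures rest on the assumed splits, bivariate normality and no mean change. They are per product group and at the threshold, and they include any real dietary change. They show what a pass is compatible with and do not predict this study's results. This is a secondary objective. The change is worth making because it alters what the study can conclude about reproducibility.

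**What to change.** In the sub-objective and in Section 8:

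1. State whether grams or colour scores are correlated, and name the coefficient.
2. Keep the 0.75 correlation criterion.
3. For each product group with colour categories, add the percentage of participants with the same colour in both series with a 95% CI, the 3x3 spring-autumn table and a chance-corrected weighted kappa.
4. State that a group's colour classification will not be called reproducible on the correlation alone or on raw agreement alone. If the 75% goal is applied to retest, read it together with kappa and describe it as stability over three to six months.

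The cost is a wording change and one extra table per group from data already being collected. The downside is a less favourable reproducibility statement for some groups.
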